Change in eye assessments will be summarized using descriptive statistics (mean, standard deviation, coefficient of variation (%CV), median, minimum, and maximum). The primary endpoint is the difference between SJP-0132 and placebo in changes in eye dryness symptom (visual analog scale [VAS]). Secondary endpoints are changes in dry eye signs (vital staining of cornea, conjunctiva and lid margin, tear film break-up time (TFBUT), and changes in dry eye symptoms (VAS [ie, severity of eye dryness, discomfort, burning/stinging, sticky feeling, foreign body sensation, itching, pain, blurred vision, and sensitivity to light], ocular surface disease index [OSDI[®]], Dry eye Questionnaire 5 [DEQ-5] scores).

Pharmacokinetic Analysis:

Plasma samples will be analyzed to determine the concentration of SJP-0132. Pharmacokinetic variables will be calculated using non-compartmental analysis. Part A: C_{max} , t_{max} , t_{last} , AUC_{0-last} , $AUC_{0-\infty}$, $AUC_{\%extrap}$, $t_{1/2}$, $AUMC_{0-last}$, $AUMC_{0-\infty}$, MRT_{0-last} , $MRT_{0-\infty}$, Vd/F , CL/F , $C_{max,norm}$, $AUC_{0-last,norm}$, $AUC_{0-\infty,norm}$. Part B: C_{max} , t_{max} , t_{last} , AUC_{0-last} , $C_{max,norm}$, and $AUC_{0-last,norm}$ on Day 1, C_{trough} on Days 2, 4 and 8, and Rac . The PK data will be summarized using descriptive statistics and will also be displayed graphically as appropriate.

2. Schedule of Activities (SoA)

Part A (SAD)	Screen	Run-in	Check In	Treatment Phase						Check Out
				Day 1						
Procedure	Day -30 to Day -15	Day -14 (+2) ⁵ to Day -2	Day -1	0 h	0.25 h	1 h	2 h	4 h	8 h	12 h
Informed Consent / HIPAA	X									
Demography	X									
Medical / Surgical History	X		X							
Inclusion/Exclusion Criteria	X		X							
Physical Examination ¹	X			X		X				X
Height	X									
Weight	X		X							
Vital signs ²	X		X	X	X	X	X	X	X	X
DEQ-5 ³	X		X							
VAS ³	X		X	X	X	X	X	X	X	X
OSDI ^{®3}	X		X							
Hematology, Serum Chemistry, Urinalysis	X		X							X
Serology (HIV, HBsAg, HCV)	X									
Serum pregnancy test and FSH (WOCBP only)	X									
Pharmacokinetic Sampling				X	X	X	X	X	X	X
Urine drug and alcohol screen	X		X							
Urine Pregnancy Test			X							
Visual Acuity (Snellen)	X		X							X X
Slit lamp biomicroscopy (w/out mydriatics)	X			X		X	X			X X
Matrix Metalloproteinase-9 (MMP-9) ⁴	X		X							
TFBUT	X			X			X			X X
Corneal fluorescein staining (Baylor)	X		X	X			X			X X
Lissamine green staining (Baylor + Lid Margin)	X			X						
Aesthesiometer	X									

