The first cohort randomized in Part B (Cohort 5) will receive the second maximum acceptable concentration of SJP-0132 ophthalmic [REDACTED] or placebo [REDACTED] [REDACTED] for 4 weeks. The second cohort randomized in Part B (Cohort 6) will receive the maximum acceptable dose of SJP-0132 ophthalmic [REDACTED] or placebo [REDACTED] for 4 weeks. All treatments will be administered in both eyes.

After Cohort 5 completes the 7-day inpatient assessment of SJP-0132 ophthalmic [REDACTED] or placebo, the Investigator and the Sponsor will assess the data (AEs, clinical laboratory results, vital signs, ophthalmic examinations) to confirm adequate safety and tolerability before allowing a cohort of the next dose level (Cohort 6) to begin. A written report will be provided.

All subjects who complete the Day 29 ± 2 EOS visit, will receive a follow-up telephone call on Day 36 ± 2 to review AEs and medication use.

For any subjects who receive at least one dose of study drug and discontinue or withdraw from study participation prior to the Day 29 ± 2 EOS visit, subjects should complete the EOS visit at the time of discontinuation/withdrawal. Discontinued/withdrawn subjects will also be contacted by telephone 7 days later for follow-up.

Pharmacokinetic (PK) blood draws will be collected prior to dosing on Days 1, 2, 4, and 8, and after dosing on Day 1 at timepoints specified in SoA.

For all subjects in Part A and Part B, the following eye assessments will be done according to the SoA: VAS, visual acuity (by Snellen), corneal aesthesiometry (Cochet-Bonnet), DEQ-5, OSDI[®], slit-lamp biomicroscopy, VAS with anesthesia, intraocular pressure (iCare), fluorescein staining (Baylor Scales), lissamine green staining (Baylor Scales +lid margins [lid wiper epitheliopathy]), Schirmer I test (without anesthesia), and tear film break up time (TFBUT), ophthalmoscopy, and matrix metalloproteinase-9 (MMP-9). All ocular exams will be completed for both eyes (study eye and non-study eye) at all timepoints.

For all subjects in Part A and Part B, the following safety assessments will include changes in vital signs (blood pressure, heart rate, oral body temperature (°C), respiratory rate), clinical laboratory results (hematology, clinical chemistry, and urinalysis), adverse events (AEs), concomitant medication use, physical examinations. Additionally, the subjects' overall ocular irritation will be assessed.

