7.5. Method of Treatment Assignment

Subjects will be randomly assigned to SJP-0132 or placebo using a computer-generated randomization scheme.

Part A: 4 cohorts consisting of 8 subjects each (non-Japanese), with 6 subjects randomized to SJP-0132 ophthalmic [REDACTED] and 2 randomized to placebo.

- Cohort 1: 0.03% SJP-0132 / Placebo
- Cohort 2: 0.1% SJP-0132 / Placebo
- Cohort 3: 0.3% SJP-0132 / Placebo
- Cohort 4: 1% SJP-0132 / Placebo

Part B: 2 cohorts consisting of 30 subjects each (9 Japanese and 21 non-Japanese) 20 randomized to SJP-0132 ophthalmic [REDACTED] and 10 randomized to placebo:

Cohort#	Active		Placebo		Total
	JP	Non-JP	JP	Non-JP	
5	6	14	3	7	30
6	6	14	3	7	30
Total	12	28	6	14	60

JP = Japanese

Doses selected for Part B will be determined after evaluation of safety and tolerability in Part A. The first cohort randomized in Part B (Cohort 5) will receive the second maximum acceptable concentration of SJP-0132 ophthalmic [REDACTED] or placebo [REDACTED]

[REDACTED] 4 weeks. The second cohort randomized in Part B (Cohort 6) will receive the maximum acceptable dose of SJP-0132 ophthalmic [REDACTED] or placebo [REDACTED] for 4 weeks.

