10.1. General Considerations

The primary statistical analysis of the data will be descriptive in nature. For continuous variables this means calculation of the number of observations, mean, standard deviation, median, minimum, and maximum. Categorical variables will be summarized by subject counts and related percentages. For ordinal-scaled variables, a combination of the above may be employed as appropriate: frequency and percentage of observations within a category and means and standard deviations of the scores of the categories. For categorical and ordinal variables, percentages will be calculated based on non-missing data.

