10.4. Statistical Analyses

All the analysis will be carried out separately for Part A and Part B upon completion of the study visit (EOS). Data will be summarized by cohort and across all active dose levels. Complete details of the statistical analyses to be performed will be documented in a statistical analysis plan, which will be completed prior to database lock. This document will include more detail of analysis populations, summary strategies, and any amendments to the proposed analyses listed here, if necessary. Any changes to the statistical analysis plan will be outlined in the final study report.

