10.4.1. Efficacy Analyses

This section is a summary of the planned statistical analyses of the primary and secondary endpoints. All analyses, summaries, and listings will be performed using SAS® software (Version 9.4 or higher version)

Endpoint	Statistical Analysis Methods
Primary	
Change from baseline (predose on Day 1) in eye dryness symptom (visual analog scale [VAS]) at 4 hours on Day 29
 
Change from baseline (predose on Day 1) in corneal fluorescein staining (CFS) score at the central zone on Day 29

Secondary	
Changes from baseline in dry eye signs: CFS scores at the central, superior, inferior, nasal, temporal and total zones, conjunctival lissamine green staining (CLGS) scores at each of 3 nasal and 3 temporal zone and total zone of bulbar conjunctiva, lid wiper epitheliopathy score, and tear film break-up time (TFBUT) at each time point tested
 
Changes from baseline in dry eye symptoms (VAS [ie, severity of eye dryness, discomfort, burning/stinging, sticky feeling, foreign body sensation, itching, pain, blurred vision, and sensitivity to light], ocular surface disease index [OSDI®], Dry eye Questionnaire 5 [DEQ-5] scores) at each time point tested
 
Biomarker (Matrix Metalloproteinase-9 (MMP-9), InflammaDry®)

The study eye will be the eye with the greater central zone corneal fluorescein staining score at predose on Day 1. If both eyes meet all of the inclusion and none of the exclusion criteria and the central zone corneal fluorescein staining scores are equal, the right eye (OD) will be designated as the study eye for the duration of this study.

The fellow eye (non-study eye) will be treated with the product as per the assigned dosing schedule.

Change in eye assessments will be summarized using descriptive statistics (mean, standard deviation, coefficient of variation (%CV), median, minimum, and maximum).

For this study co-primary endpoints will be as follows: the differences between SJP-0132 and placebo in changes from baseline in eye dryness symptom (visual analog scale [VAS]) and change from baseline (predose on Day 1) in corneal fluorescein staining (CFS) score at the central zone on Day 29.

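### Primary efficacy is worded as a difference from placebo, but only per-group summaries of change are named; reporting the baseline-adjusted difference with its interval would be a cheap improvement

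*Combined protocol and SAP*

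**What the plan says.** **The endpoint.** Section 10.4.1 states: "For this study co-primary endpoints will be as follows: the differences between SJP-0132 and placebo in changes from baseline in eye dryness symptom". The sentence then adds change from baseline in central corneal fluorescein staining (CFS) on Day 29. The Efficacy Analysis paragraph of the synopsis agrees for the symptom score only: "The primary endpoint is the difference between SJP-0132 and placebo in changes in eye dryness symptom". The objectives tables in the synopsis and in Section 4, and the Primary row of the table in Section 10.4.1, list both endpoints simply as change from baseline, with no comparison of arms.

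**The method.** Section 10.1 says "The primary statistical analysis of the data will be descriptive in nature". For efficacy, Section 10.4.1 says "Change in eye assessments will be summarized using descriptive statistics (mean, standard deviation, coefficient of variation (%CV), median, minimum, and maximum". Section 10.4 sets the grouping, "Data will be summarized by cohort and across all active dose levels", keeps Parts A and B separate, and says that complete details will be "documented in a statistical analysis plan, which will be completed prior to database lock".

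**The design.** Section 7.5 gives Part B as "2 cohorts consisting of 30 subjects each (9 Japanese and 21 non-Japanese) 20 randomized to SJP-0132 ophthalmic", with the other 10 in each cohort on placebo. The cohorts are sequential: Section 5.1 requires a safety review of Cohort 5 "before allowing a cohort of the next dose level (Cohort 6) to begin".

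**The concern.** Means and standard deviations of change describe each group. They do not state the difference that Section 10.4.1 and the synopsis call primary, or how precisely it is known. A reader could rebuild the raw difference and its standard error from n, mean and SD, but could not rebuild a baseline-adjusted one.

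The placebo group is only partly settled. For a single dose, summarising by cohort, with placebo randomised inside each cohort, leans toward the 10 placebo subjects of that cohort. For the summary across active doses, no placebo group is named. Own-cohort and pooled placebo give different estimates, so the choice is better fixed before unmasking than after it.

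**Working it through.** **1. The plan's own figure.** Part A is 4 × 8 = 32 and Part B is 2 × (20 + 10) = 60, total 92, as in Section 10.2. Part B has 40 active and 20 placebo subjects. No power calculation exists to reproduce. The documents give no SD of change, so results are in units of that SD. Both primary endpoints are Day 29 measures, so only Part B matters.

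**2. Unadjusted precision.** In one model with four groups (two cohorts × active or placebo), 95% half-width = t(0.975, df) × √(1/n₁ + 1/n₂). At full enrolment df = 60 − 4 = 56 and t = 2.003. The loss columns assume 10% or 20% lost from every group (df 50 and 44).

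| Contrast | Full | 10% loss | 20% loss |
|---|---|---|---|
| One dose v own-cohort placebo (20 v 10) | 2.003 × √0.15 = 0.776 | 0.820 | 0.873 |
| One dose v pooled placebo (20 v 20) | 2.003 × √0.10 = 0.633 | 0.670 | 0.713 |
| All active v all placebo (40 v 20) | 2.003 × √0.075 = 0.549 | 0.580 | 0.617 |

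Full enrolment is the best case, since Section 10.2 expects about 60 completers and Section 8 does not replace withdrawals. As an illustration, an observed 0.5 SD difference for one dose would carry an interval of 0.5 ± 0.776, or −0.28 to 1.28 SD.

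**3. Own-cohort against pooled placebo.** The two estimates for a dose differ by half the gap between the two placebo means. With no true shift between cohorts, that has SD √(1/10 + 1/10)/2 = 0.224 SD. If the true placebo shift is d, the pooled contrast has mean squared error 0.10 + d²/4, against 0.15 for own-cohort. Pooling is better only if d < √0.20 = 0.447 SD. The trial estimates that shift to within 2.003 × √0.20 = 0.896 SD, so its data cannot settle the question.

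The comparison across doses is different. Both cohorts are 2:1, so 40 v 20 equals the average of the two own-cohort differences: √(0.15/4 + 0.15/4) = √0.075. A shift common to both arms of a cohort cancels.

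**4. What baseline adjustment could gain.** Let ρ be the correlation between baseline and Day 29, and k the baseline SD divided by the Day 29 SD. The documents give neither. The variance of the adjusted relative to the raw analysis of change is (1 − ρ²)/(1 + k² − 2ρk).

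| | ρ = 0.3 | ρ = 0.5 | ρ = 0.7 |
|---|---|---|---|
| k = 1 | 0.65 | 0.75 | 0.85 |
| k = 0.7 | 0.85 | 0.95 | 1.00 |
| k = 0.5 | 0.96 | 1.00 | 0.93 |

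The saving is therefore 0 to 35%. The entry limits in Section 6.1 on dryness score and central staining may narrow the baseline spread, which lowers k and points toward the small-gain end.

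**5. Adjusted half-width, one dose v own-cohort placebo.** Two covariates leave df = 54 and t = 2.005. Chance baseline imbalance adds a factor of about √(1 + 1/54) = 1.009.
- Ratio 1.00: 2.005 × √0.15 × 1.009 = 0.784.
- Ratio 0.65: 0.784 × √0.65 = 0.632.

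A simulation of the full model with the Section 7.5 allocation (1,500 runs per setting) gave 0.627 to 0.781. The Japanese share is 6/20 = 3/10 = 30% in every group, so at full enrolment that covariate costs a degree of freedom without disturbing the contrasts.

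**The case against.** - **The study is openly descriptive.** Sections 10.1 and 10.2 declare a descriptive, feasibility-sized study. A reader might infer that a missing hypothesis test or power calculation is a defect. The documents promise neither, and this point asks for neither.
- **Detail is deferred.** Section 10.4.1 calls itself a summary, and Section 10.4 leaves full detail to an SAP due before database lock. The supplied file holds no separate SAP text, so nobody can say that the SAP is silent. The methods column in Section 10.4.1 shows no method, but text may have been lost in extraction; the prose carries the point alone. This objection stands against calling the gap an error, though not against recommending a better analysis while it can still be adopted.
- **The endpoint wording is mixed.** A reader might infer that both co-primary endpoints are firmly defined as differences. In Section 10.4.1 the word plainly governs the symptom score; extending it to CFS is reasonable but looser. For an endpoint defined as change, summaries of change are a matching analysis. This stands, and is why the wording needs aligning.
- **The comparator is not wide open.** For single doses, own-cohort placebo is the natural reading. The real gap is the summary across doses.
- **The intervals are wide because the trial is small.** A reader might infer that the half-widths measure harm done by the omission. They reflect sample size and would be the same whether or not an interval is printed.
- **ANCOVA may gain nothing.** True at several of the assumed settings. An unadjusted difference with its interval would close the reporting gap alone; adjustment is a low-cost addition that may help.

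**Conclusion.** The point holds as a cheap improvement, with medium confidence. Section 10.4.1, and the synopsis for the dryness score, word the primary quantity as a difference from placebo, while the supplied text names only per-group summaries of raw change. Reporting the difference directly would show precision of 0.78, 0.63 or 0.55 SD according to the contrast, assuming full enrolment and a common SD. The variance saving of 0 to 35% rests on assumed ρ of 0.3 to 0.7 and k of 0.5 to 1. The stronger conclusion, that the plan is wrong or has no valid primary analysis, is not supported: a descriptive analysis is declared, the raw difference can be recovered from its outputs, and the SAP can settle the rest in a double-masked trial.

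**What to change.** In Section 10.4.1 or the SAP, before unmasking:

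1. Align the endpoint wording across the synopsis (objectives table and Efficacy Analysis), Section 4 and Section 10.4.1, including whether CFS is meant as a difference from placebo.
2. For Day 29 4-hour eye dryness VAS, and for Day 29 central CFS in the study eye, fit an ANCOVA of change on the four treatment-by-cohort groups, with the Day 1 predose value of the same measure and Japanese/non-Japanese as covariates. Report differences with 95% intervals, labelled as estimation without formal testing.
3. Make each dose against its own-cohort placebo the default contrast. Show pooled placebo as supportive, under a stated assumption of no shift between cohorts, and take all active against placebo from the same model.
4. Show CFS category frequencies as well, which Section 10.1 already allows.
5. Name the analysis set, since Section 10.3 defines a full analysis set and a per protocol set without assigning either to efficacy. Say also how an end-of-study visit brought forward by withdrawal (Sections 5.1 and 8) enters the Day 29 analysis.

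The cost is some wording and a few outputs, with no new data or subjects. The covariates use 2 degrees of freedom; if baseline carries little information the interval can be marginally wider (0.784 against 0.776 SD). A linear model is an approximation for an ordinal CFS score.

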10.4.2. Safety Analyses

All safety analyses will be performed on the Safety Population.

Endpoint	Statistical Analysis Methods
Primary	The number and severity of AEs including abnormal changes from baseline in clinical laboratory results, vital signs, and physical and ophthalmologic examinations

Safety assessments and changes from baseline in vital signs, clinical laboratory results, adverse events (AEs), treatment-emergent AEs (TEAEs), will be summarized using descriptive statistics as outlined in the statistical analysis plan including but not limited to (mean, standard deviation, coefficient of variation (%CV), median, minimum, and maximum). Concomitant medications and physical examination findings will be listed.

10.4.3. Pharmacokinetic Analyses

Plasma samples will be analyzed to determine the concentration of SJP-0132. Pharmacokinetic variables will be calculated using non-compartmental analysis.

Individual PK concentrations and PK parameters will be listed. The PK data will be summarized descriptively by dose/cohort using appropriate statistics (eg, N, n, arithmetic mean, SD, minimum, median, maximum, geometric mean [PK parameters only, as appropriate], and coefficient of variance [CV%]). Graphical presentations will include by-subject and mean concentrations plots which will be presented on linear and semi-logarithmic scales. Scatterplots of individual and geometric mean exposure parameters [AUC_{0-∞}, AUC_{0-last}, and C_{max}] will be presented by dose. Additional graphical presentations of PK data may be added at the discretion of the PK scientist

Part A: C_{max}, t_{max}, t_{last}, AUC_{0-last}, AUC_{0-∞}, AUC%_{extrap}, t_{1/2}, AUMC_{0-last}, AUMC_{0-∞}, MRT_{0-last}, MRT_{0-∞}, Vd/F, CL/F, C_{max,norm}, AUC_{0-last,norm}, AUC_{0-∞,norm}.

Part B: Part B: C_{max}, t_{max}, t_{last}, AUC_{0-last}, C_{max,norm}, and AUC_{0-last,norm} on Day 1, C_{trough} on Days 2, 4 and 8, and Rac.

11. References

Gayton JL. Etiology, prevalence, and treatment of dry eye disease. *Clinical Ophthalmology* 2009;3 405–412

12. Appendices

Appendix 1: Abbreviations and Terms

Abbreviation	Definition
AE	Adverse event
AUC	Area under the plasma concentration-time curve
AUC ₀₋₁₆	Area under the plasma concentration-time curve from time 0 to 16 hours
AUC _{0-last}	Area under the plasma concentration-time curve from time 0 to time of the last quantifiable concentration
AUC _{0-∞}	Area under the plasma concentration-time curve from time 0 to infinite time
AUC _{0-last,norm}	AUC _{0-last} divided by dose per body weight
AUC _{0-∞,norm}	AUC _{0-∞} divided by dose per body weight
AUC _{%extrap,}	Percentage of AUC _{0-∞} that is due to extrapolation beyond t _{last}
AUMC _{0-last}	Area under the moment curve from time 0 to time of the last quantifiable concentration
AUMC _{0-∞}	Area under the moment curve from time 0 to infinite time
CFS	Corneal fluorescein staining
CLGS	conjunctival lissamine green staining
CL/F	Apparent total body clearance
CL _T	Total plasma clearance
C _{max}	Maximum plasma concentration
C _{max,norm}	C _{max} divided by dose per body weight
C _{trough}	Minimum (predose) plasma concentration during repeat dosing
%CV	Coefficient of variation, percent
CYP	Cytochrome P-450
DED	Dry Eye Disease
DEQ-5	5-item dry eye questionnaire
DEWS	International Dry Eye Workshop
F	Bioavailability
GLP	Gppd Laboratory Practice
IC ₅₀	Concentration producing inhibition in 50% of population tested
IOP	Intraocular pressure
IV	Intravenous
JP	Japanese
MRT _{0-last}	Mean residence time from 0 to time of last quantifiable concentration

Abbreviation	Definition
$MRT_{0-\infty}$	Mean residence time from 0 to infinite time
[REDACTED]	[REDACTED]
OD	Oculus dexter (right eye)
OSDI	Ocular Surface Disease Index
[REDACTED]	[REDACTED]
PK	Pharmacokinetic(s)
[REDACTED]	[REDACTED]
Rac	Accumulation ratio
SAE	Serious adverse event
SoA	Schedule of Activities
[REDACTED]	[REDACTED]
SPK	Superficial punctate keratitis
[REDACTED]	[REDACTED]
$t_{1/2}$	Apparent elimination half-life
TEAE	Treatment-emergent adverse event
TFBUT	tear film break up time
[REDACTED]	[REDACTED]
t_{last}	Time to last quantifiable concentration
t_{max}	Time to reach the maximum plasma concentration
[REDACTED]	[REDACTED]
VAS	Visual analog scale
Vd_{ss}	Steady-state volume of distribution
Vd/F	Apparent volume of distribution
WOCBP	Woman of child-bearing potential

Appendix 2: Clinical Laboratory Tests

The tests detailed below will be performed by the local laboratory.

Additional tests may be performed at any time during the study as determined necessary by the investigator or required by local regulations.

Protocol-Required Safety Laboratory Assessments

Laboratory Assessments	Parameters		
Hematology	Platelet Count	RBC Indices: MCV MCH %Reticulocytes	WBC Count with Differential: Neutrophils Lymphocytes Monocytes Eosinophils Basophils
	RBC Count		
	Hemoglobin		
	Hematocrit		
Clinical Chemistry	BUN Potassium Creatinine Sodium Glucose (fasting) Calcium Total Protein		Aspartate Aminotransferase (AST)/ Serum Glutamic-Oxaloacetic Transaminase (SGOT) Alanine Aminotransferase (ALT)/ Serum Glutamic-Pyruvic Transaminase (SGPT) Alkaline phosphatase Total and direct bilirubin
Routine Urinalysis		
Specific gravitypH, glucose, protein, blood, ketones, bilirubin, urobilinogen, nitrite, leukocyte esterase by dipstickMicroscopic examination (if blood or protein is abnormal)	
Other Screening Tests		
Follicle-stimulating hormone and estradiol (as needed in women of non-childbearing potential only)Urine drug screen (to include at minimum: amphetamines, barbiturates, cocaine, opiates, cannabinoids and benzodiazepines)]Alcohol urine testSerum human chorionic gonadotropin (hCG) pregnancy test (as needed for women of childbearing potential) at Screening and Day 29 (Part B). Urine pregnancy test at Day -1.Serology (HIV antibody, hepatitis B surface antigen [HBsAg], and hepatitis C virus antibody)	

Investigators must document their review of each laboratory safety report.

